All trial participants will further be asked about existing clinical symptoms before drug administration. Additionally, they will be asked to provide subjective short-term (*e.g.* convenience of treatment) and long-term (*e.g.* effectiveness in reducing symptoms) treatment satisfaction embedded in the re-assessment questionnaires. As a measure of patient-rated physical functioning and wellbeing all children (6-16 years) will be administered a questionnaire before, 6 and 12 months after treatment, based and adapted from tools already validated in school-aged children from rural settings in Côte d'Ivoire [23]. Before application this tool will be adapted to local conditions of Lao PDR and pre-tested in a comparable school-aged population not otherwise involved in this trial. To adjust for known influencing factors with regard to reinfection and morbidity [24, 25] in the subsequent analysis and to identify risk factors for residual infections [26] a household-based questionnaire will be administered to one adult member of each participating household, assessing information on socioeconomic characteristics, access to sanitation and water facilities as well as hygiene behavior.

4.3.2 Assessment of efficacy and other benefits after treatment

The efficacy of the treatment will be determined 21 days post-treatment by collecting another two stool samples which will be microscopically examined for *T. trichiura* using duplicate Kato-Katz thick smears and potential

co-infection with *S. stercoralis* applying the Baermann technique and the urine-based ELISA assay. Participants will be considered *T. trichiura* cured if no eggs have been found in the stool. EPG will be assessed by adding up the egg counts from the quadruplicate Kato-Katz thick smears and multiplying this number by a factor of six. Geometric and arithmetic mean egg counts will be calculated for the different treatment arms before and after treatment to assess the corresponding ERRs. The stool samples collected 21 days post-treatment for efficacy assessment will further be re-tested with the same rapid diagnostic test (including PCR and microbiome sampling) and immunoassay used at baseline to determine fecal occult blood and calprotectin levels. Frequencies of subjects found positive with either of the two markers and by intensity category for calprotectin will be calculated by treatment arm.

At the end of the study (approximately 12 months post-treatment) all participants remaining positive for *T*. *trichiura* and other soil-transmitted helminths will be treated with albendazole-ivermectin, the currently best approved and recommended treatment against *T. trichiura* [27].

Potential extended effects on follow-up helminth prevalences will be assessed using the same methodological approach as used for the efficacy assessment and will be based on stool samples collected 6 and 12 months post-treatment. Likewise fecal occult blood and calprotectin will be re-determined on the same stool samples.

To assess eventual reduction in morbidity and improvement in nutritional indicators all trial participants will be asked to provide another finger-prick blood sample at the 6 and 12 month follow-up for Hb measurement and rapid diagnostic testing (*i.e.* malaria) and once more a venous blood sample for micronutrient/blood parameter evaluation at all three follow-up time points, respectively. Anthropometric measurement including height, weight, MUAC and skinfold thickness will be repeated on the same occasion. Children (6-16 years) will be asked to re-assess their own physical functioning in repeated questionnaire interviews during these two last follow-ups. Long-term satisfaction with the treatment will be asked 6 months post-treatment. Mean values for continuous outcomes and frequencies for binary/categorical outcomes will be calculated for each treatment arm and follow-up time point and compared using descriptive and repeated measurement analysis as detailed in section 7.3.

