This important milestone paves the way for further, standardized trials to evaluate the efficacy of this combination among school-aged children in a range of epidemiological settings. In addition, the combination should be evaluated among adults, as there is growing interest in broadening deworming to include adults in order to move from morbidity control toward interruption of transmission [13, 14].

In the proposed work, three trials are planned across a range of transmission settings, including Côte d'Ivoire, Lao PDR, and Pemba (Tanzania). Follow-up will be conducted at 1, 6, and 12 months to inform treatment frequency. Results from these trials will inform decisions on how the combination could be introduced into

Page 143 of 176

existing mass drug administration (MDA) programs and therefore provide a valuable adjunct tool for interrupting STH transmission.

3. Trial objective and purpose

The overall goal of the study is to assess the efficacy and safety of co-administered albendazole and ivermectin versus albendazole monotherapy (standard of care) against *T. trichiura* infections in children and adults (6-60 years) in different transmission settings and geographies.

We hypothesize that albendazole-ivermectin has a higher efficacy against *T. trichiura* infections than albendazole alone, and hence, the efficacy against all three STH species (*A. lumbricoides*, *T. trichiura*, and hookworm) and *Strongyloides stercoralis* will be increased.

The **primary objective** of the trial is to comparatively assess the efficacy in terms of CR against *T. trichiura* infections among school-aged children and adults from three different epidemiological settings and monitored over a 12-month period of the following two oral treatment regimens:

- Albendazole/ivermectin combination
- Albendazole monotherapy

The secondary objectives of the trial are:

- a) To evaluate the safety and tolerability of the treatment regimens
- b) To compare the ERRs of the treatment regimens against *T. trichiura*
- c) To determine the CRs and ERRs of the drugs in study participants (6-60 years) infected with hookworm, *A. lumbricoides* and *S. stercoralis*
- d) To investigate potential extended effects on follow-up helminth prevalences (6 and 12 months post-treatment) of the two treatment regimens (as assessed among participants with cleared infection on days 21 and 180)

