At baseline, all participants will be asked to provide two stool samples of at least 15 grams each (within a maximum of 5 days). From every stool specimen, duplicate Kato-Katz thick smears (41.7 mg each) [15] will be prepared and read under a microscope for eggs of T. trichiura, A. lumbricoides and hookworm by experienced technicians. A small amount of feces (~10 mg and $60\mu g$, respectively) will further be tested on fecal occult blood and calprotectin as proxies for gut morbidity and inflammation using a rapid diagnostic test and an immunoassay, respectively [16]. Additionally, a portion of 1.5-2 g of stool from each specimen will be frozen and preserved in 70% ethanol, respectively and shipped to a reference laboratory at the Swiss Tropical and Public Health Institute (Swiss TPH, Basel, Switzerland) for microbiome and PCR analysis [17]. While discrimination of hookworm species via morphological comparison during microscopy of Kato-Katz slides is not feasible [18], PCR will allow to accurately determining efficacy and for further classification of hookworm infection into the three species N. americanus, A. duodenale and A. ceylanicum. The remains of each stool sample (ideally 10 to 20 g) will be processed by the Baermann technique for identification of S. stercoralis infections and be recorded qualitatively as larvae-positive or negative. Urine samples from each participant will be collected together with the 2nd stool sample, fixed and transferred to a laboratory at Khon Kaen University in Thailand for subsequent detection of S. stercoralis antibodies using a novel ELISA-based assay. At baseline and in the first follow-up (3 weeks post treatment) an additional portion of the second stool sample (1.5-2 g) from a

Page 146 of 176

subsample of 10 participants identified with heavy intensity infections in each case (as assed on the first sample) will be preserved in 95% ethanol, shipped to the same reference laboratory at Swiss TPH in Switzerland and subjected to deep sequencing for characterization of *T. trichiura* strains and investigation of potential resistance markers [19]. A subsample of 30 participants in each treatment arm will be asked to provide a daily stool sample for a period of up to 4 weeks to monitor dynamics of *T. trichiura* egg output for subsequent determination of the optimal timing for drug efficacy assessment as has been done for other STH species earlier [20].

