7.2 Justification of number of trial subjects

Based on available summarized efficacy measures from a recent review [1] and the published literature, we assume that the CR of albendazole against *T. trichiura* is 30% compared to 50% in the albendazole-ivermectin treatment regimen. To detect a difference with 90% power at a two-sided 5% significance level, we require 121 participants per study arm and 143 to account for potential loss to follow-up of 15%. We further assume the same treatment efficacy in the mid-term treatment and a 6-months reinfection risk of 10%. Consequently we expect a proportion of negative patients after 12 months of 44% in the albendazole arm and of 65% in the albendazole-ivermectin arm resulting in a required sample size of 111 participants per arm. To account for a loss to follow-up of 30% after 6 months and 40% at final assessment (12 months) we aim to recruit 300 participants in each treatment group (600 in total) in each country.

Subgroup analysis will be conducted stratifying the study population by age category (school-aged and adults). For the subgroup analysis we will pool the data from all 3 countries to ensure sufficient statistical power.

Page 155 of 176

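### The 6- and 12-month extended-effect comparison defines clearance by four Kato-Katz slides alone, so missed persistent infections count as reinfection, by an amount and in a direction between arms that the documents cannot settle

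*Combined protocol and SAP*

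**What the plan says.** - **Cure at day 21** (section 4.3.2 of each protocol). Two stools with duplicate smears each are examined, and a participant counts as "cured if no eggs have been found in the stool". Egg counts from the four slides are summed, "multiplying this number by a factor of six", so one egg seen equals 6 EPG.
- **Objective (d)** (section 3, Trial objective and purpose). Extended effects at 6 and 12 months are "as assessed among participants with cleared infection on days 21 and 180". Cleared is not defined separately. Section 4.3.2 adds that these effects "will be assessed using the same methodological approach as used for the efficacy assessment".
- **Reinfection and residual infection.** Section 4.3.1 describes participants re-treated after month 6 as re-infected. It plans adjustment for factors that influence reinfection and morbidity, and a household questionnaire "to identify risk factors for residual infections". Section 7.2 assumes "a 6-months reinfection risk of 10" percent.
- **PCR** (section 4.3.1). An aliquot is kept from every stool, and the sampling is repeated at days 21, 180 and 360. The text says "PCR will allow to accurately determining efficacy". Its stated uses are a comparison of cure rates between methods (objective e), hookworm species (objective f) and a separate secondary endpoint in the SAP. Nothing links it to the cleared group.
- **SAP.** It covers the data collected three weeks after treatment. The Time and Events Table marks days 180, 185 and 360 as outside its scope.

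**The concern.** The extended-effect question is whether people whose infection was removed stay free of it longer on one regimen than on the other. That requires the cleared group to be free of infection at the start. Four 41.7 mg smears examine about 0.167 g of stool, so a light persistent infection can give four negative slides. Such a person is recorded as cleared at day 21. If positive at month 6, the same person is read as reinfected, although nothing new was acquired.

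At stake is the between-arm comparison under objective (d). If the arms differ in the share of undetected persistence among their cleared participants, they will differ in apparent reinfection even when true reinfection is equal. Any analysis of risk factors for residual infection, or of reinfection, would mix the two outcomes. The plan already collects a second test on the same stools that could separate much of this, but gives it no such role.

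**Working it through.** **1. The plan's own figures.** With unpooled variance, n = [p1(1−p1) + p2(1−p2)](1.960 + 1.282)² / d².
- 30% v 50%: 120.8, so 121 per arm; 121/0.85 gives 143.
- Negative at 12 months = [0.9c + (1 − 0.9c)c] × 0.9. This gives 44.0% for c = 0.30 and 65.25% for c = 0.50, and n = 110.2, so 111.

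All match section 7.2. The calculation uses one 10% reinfection risk in both arms and treats every Kato-Katz negative as uninfected.

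**2. Share of the cleared group still infected.** Let CR be the observed cure rate and s the sensitivity of the four slides, with perfect specificity assumed. Observed positives are 1 − CR = s × (truly infected), so missed infections are (1 − CR)(1 − s)/s. As a share of those called cleared:

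f = (1 − CR)(1 − s) / (s × CR)

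CR is 30% (albendazole) and 50% (combination), from section 7.2 and taken as observed rates. The documents give no s; the values below are assumptions.

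**3. Apparent reinfection at month 6.** With true reinfection of 10% and every persistent infection detected at month 6 (assumed), apparent risk = f + (1 − f) × 0.10.

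| s, albendazole / combination | f, albendazole / combination | Apparent reinfection, albendazole / combination |
|---|---|---|
| 0.95 / 0.95 | 12.3% / 5.3% | 21.1% / 14.7% |
| 0.90 / 0.90 | 25.9% / 11.1% | 33.3% / 20.0% |
| 0.95 / 0.90 | 12.3% / 11.1% | 21.1% / 20.0% |
| 0.98 / 0.90 | 4.8% / 11.1% | 14.3% / 20.0% |
| 0.95 / 0.85 | 12.3% / 17.6% | 21.1% / 25.9% |

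First row, albendazole: 0.70 × 0.05 / (0.95 × 0.30) = 0.123, and 0.123 + 0.877 × 0.10 = 0.211. If only 80% of persistent infections are detected at month 6, the first row becomes 18.6% / 13.7% and the fourth 13.3% / 17.8%.

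**4. What decides the direction.** The combination has the larger share only if its odds of a missed infection, (1 − s)/s, exceed those of albendazole by more than (0.70/0.30)/(0.50/0.50) = 2.33. If albendazole sensitivity is 0.95, combination sensitivity must be below 0.891; if it is 0.98, below 0.955.

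**5. Numbers involved.** With 300 per arm per country and 30% loss, 210 per arm remain at month 6, of whom 63 and 105 would be in the cleared groups. Misclassified participants number about 7.7 and 5.5 at 0.95/0.95, and 3.0 and 11.7 at 0.98/0.90.

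**6. Effect of adding PCR.** Suppose PCR finds a share q = 0.80 of the missed infections and gives no false positives (both assumed). The residual share becomes f(1 − q) / [f(1 − q) + 1 − f].
- 0.95/0.95: apparent reinfection falls from 21.1% / 14.7% to 12.5% / 11.0%. The cleared group falls from 30% / 50% to 27.1% / 47.9% of those assessed.
- 0.98/0.90: it falls from 14.3% / 20.0% to 10.9% / 12.2%. The cleared group becomes 28.9% / 45.6%.

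**The case against.** **Consequences are narrow.** The primary endpoint is Kato-Katz status by definition. Re-treatment goes to every participant positive for *T. trichiura* at month 6, whatever the label. The 44% and 65% in section 7.2 are proportions negative among all participants, not reinfection among the cleared. PCR status is already a secondary endpoint and objective (e) compares it with microscopy, so the data will exist. All of this stands. It limits the point to objective (d) and related 6- and 12-month readings, where no document says how the PCR data will be used.

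**PCR is no clean reference.** It may detect dead material at day 21, perhaps to a different degree by arm, and the documents give neither its sensitivity nor its specificity. This also stands, and is why the PCR-based version should sit beside the Kato-Katz version and not replace it.

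**A reader might infer that the excess falls in the combination arm**, because its egg reduction rates (91.3–99.7%, geometric) exceed the 49.9% for albendazole and so leave lighter infections that are easier to miss. That is plausible but not established. The type of mean behind 49.9% is not stated, and the combination's arithmetic range is 85.6–97.5%. Albendazole also leaves more people infected and clears fewer, so equal sensitivity puts the excess in that arm.

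**A reader might also take the post-treatment means of 11 and 27 EPG in Table 2 as the intensity of remaining infections**, which gives a chance of four negative slides of 16% and 1% (Poisson). Those geometric means appear to cover whole arms, including the cured (37.9% and 27.5%). Removing the zeros, assuming means of log(EPG + 1), gives about 12^(1/0.621) − 1 = 54 and 28^(1/0.725) − 1 = 98 EPG among detected positives. The chance is then about 0.01% and essentially nil (Poisson), or 10% and 6% if counts are overdispersed (negative binomial, k = 1, assumed). Missed infections are lighter than detected ones, so this does not fix the sensitivity either.

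**Conclusion.** The point holds for objective (d) and for any reinfection or residual-infection analysis at 6 and 12 months. Clearance rests on four Kato-Katz slides, the objective conditions on it, and the planned PCR is not used to define it. Any sensitivity below 100% then turns some persistence into apparent reinfection. At the assumed sensitivities the distortion matters against a true 10%: 21.1% v 14.7% at 0.95 in both arms, 14.3% v 20.0% at 0.98/0.90. The first pattern would exaggerate the combination's extended benefit and the second would dilute it.

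These figures rest on cure rates of 30% and 50% taken as observed, perfect Kato-Katz specificity, equal true reinfection, detection of all persistent infections at month 6, and assumed sensitivities. They show a possible size and do not predict the result.

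The documents do not support a claim that the bias runs against the combination. Nor do they describe separate risk-factor analyses for reinfection and for residual infection: section 4.3.1 plans risk-factor identification for residual infection, and adjustment where reinfection and morbidity are concerned. The day-21 primary result is not put in doubt by this point.

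**What to change.** In section 4.3.2 of the protocols, and in an analysis plan for days 180 to 360 (which the current SAP does not cover):

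- Define cleared for objective (d) explicitly, and prespecify two versions: negative by Kato-Katz alone, and negative by both Kato-Katz and PCR on the same stools, at day 21 and at day 180.
- Report the two versions side by side, by arm, with the number of Kato-Katz-negative, PCR-positive participants in each arm. Use the same pair of definitions in any analysis of reinfection or of risk factors for residual infection.
- Describe Kato-Katz-negative, PCR-positive participants as possible residual infection, and state that PCR may detect dead material, possibly to a different degree by arm.
- Keep the primary cure rate on Kato-Katz.

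The cost is protocol and analysis-plan wording and some extra analysis. No new sampling is needed, because the aliquots are already planned at every time point. The downside is a smaller cleared group under the two-test definition.

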4.4 Measure to minimize bias

Study participants eligible for treatment will be randomly assigned to one of the treatment arms using a computer-generated stratified block randomization code. The random allocation sequence with varying random blocks of four or eight and stratified by 2 levels of baseline infection intensity (light: <1000 EPG, and moderate plus heavy: \geq 1000 EPG *T. trichiura* infections) will be provided by a statistician. The treatment arms will have an equal number of participants with light infection intensity, although the number of light versus moderate/heavy infections are not expected to be equal in each arm, depending on the distribution of infection intensity in the recruited cohort. The study will be double blinded (*i.e.* study participants and the trial team/researchers conducting the treatment and assessing the outcomes will be blinded) using repacked tablets including appearance-matched placebos.

4.5 Study duration and duration of subject participation

The trial will last fourteen months. The screening for the baseline will start three weeks prior to the treatment. Follow-up screening will take place 14-21 days, 180 days and 360 days post-treatment and last each time for about three weeks. Schedules of visits are summarized below.

4.6 Schedule of visits

Page 148 of 176

 Table 3. Schedule of visits of parallel group trial.

	Screenin g	Baseli	ne/Tr	eatment/	'Safety	Follow up					
	-21 to -1	to -1 Hours Day									
	days	0		3	24	21	180	185	360		
Diagnosis (stool and urine examination)	Х					Х	Х		Х		
Gut morbidity (stool RDTs)	Х					Х	Х		Х		
Informed consent	Х		ent								
Demographics	Х		eatm								
Medical history		Х	nd tro					ment			
Clinical examination		Х	ion a				Х	treat	Х		
Pregnancy testing		Х	mizat				Х	ve re-			
Hemoglobin measurement		Х	ando				Х	electi	Х		
Plasmodium co-infection		Х	R				Х	Š	Х		
Venous blood examination		Х				Х	Х		Х		
Physical functioning		Х					Х		Х		
Capturing AEs				Х	Х	Х					
Capturing SAE				Х	Х	Х					
Treatment satisfaction				Х		Х	Х				

5. Selection of the trial subjects

5.1 Recruitment

The study will be carried out in community members aged 6–60 years in areas with moderate to high *T. trichiura* endemicity (communities with a prevalence $\geq 25\%$) identified from earlier studies and/or based on experience of the local collaborating teams. The trial will be implemented as community-based study in order to recruit participants from a broad age range (6–60 years). Ideally, entire communities with population size of < 1000 inhabitants will be included in the study for pre-screening and identification of *T. trichiura* cases to avoid potential selection bias of households. To identify all potentially eligible households of the respective communities and its composition in terms of age groups a preceding population census will be conducted.

All adult community members, including parents/caregivers of minor participants, will be invited to participate in an information meeting to explain the purpose and procedures of the study, including potential benefits and risks. Parents/caregivers/potential participants will be encouraged to ask questions in an open discussion forum. During this session, they will be informed of preventive actions they can take to help protect their children from

acquiring *T. trichiura* and other STH infections in the future (*e.g.* adequate food, preparation and defecation behavior).

Those parents/caregivers and their children who are interested in the study will be invited to complete the process of informed consent. See section 9.3 for details on obtaining informed consent. Only those participants who have written informed consent will be assessed for study eligibility criteria during screening procedures.

5.2 Inclusion criteria

- 1. Written informed consent signed by either the participant him/herself (≥18 years of age) or by parents and/or caregivers for children/adolescents; and oral assent by child/adolescent (aged 6–17 years).
- 2. Agree to comply with study procedures, including provision of two stool samples at the beginning (baseline) and on three follow-up assessments (approximately 3 weeks, 6 months, and 12 months later).
- 3. Aged ≥ 6 to ≤ 60 years.
- 4. At least two slides of the quadruple Kato-Katz thick smears positive for *T. trichiura* and infection intensities of at least 100 EPG.

